PET/CT: Standard clinical Mayo Clinic whole-body PET/CT acquisition protocol.

PET/MR: PET/MRI myeloma acquisition study protocol:

	t inycloma acquisition study protocol.
Whole Body	
Station 1	
Station 2	
Station 3	
Station 4	
PET Task W	/hole Body
Bed 1 3:0	00
MRAC	1
AX LA	VA-Flex 1
Bed 2 4:	00
MRAC 2	
AX LAV	A-Flex 2
Bed 3 4:	00
MRAC 3	
AX LAV	A-Flex 3
Bed 4 3:	:00
MRAC 4	
AX LAV	A-Flex 4
Bed 5	3:00
MRAC	5
AX LAV	VA-Flex 5
Bed 6 3	:00
MRAC	6
AX LAV	VA-Flex 6
Bed 7 3	3:00
MRAC	7
AX LAV	VA-Flex 7

Comfort Modification: may remove body coils when acquisition of that area is complete, only if needed to keep the subject comfortable.

Schedule of Events 6.5

Study Activity	Day 0	Day 1 °	Day 2 ^f	Day 3 g
Informed consent	X			
History (confirm myeloma spectrum diagnosis). Record result on source document.	X			
Chart information recorded on study source document (height, weight, diabetic, pregnancy and breast feeding status, bone marrow biopsy (if obtained) %, beta-2-microglobulin level (if obtained).	X			
Vital signs prior to and following imaging sessions recorded on source document (sitting blood pressure, respiratory rate, temperature, heart rate)		X	X	
Finger-stick blood glucose prior to imaging		X	X	
CBC ^b , CMP ^c , SPEP ^d , Immunoglobulins, Serum free light chains. Within 4 weeks of study. Obtained as routine clinical tests, not research. Study coordinator will take data from EMR to enter on source/CRF.	X			
Pregnancy test (serum), if applicable ^a	X			
Adverse event evaluation. Results recorded on source document.		X	X	X
PET scans		X	X	
Follow-up call re: adverse events. Result recorded on source document.				X

^a Women of child bearing potential are required to have a serum pregnancy test. Women who are surgically sterile and/or greater than or equal to 12 months post-menopausal are not considered as child bearing potential. Pregnant women will not be allowed to participate in this study ^b CBC (complete blood count); red blood cells (RBCs), white blood cells (WBCs), platelets (PLTs), hemoglobin (Hgb), RBC

indices, and WBC differential

^c CMP (Comprehensive Metabolic Panel; if available, but not required to participate); Glucose, Calcium, Proteins, Albumin, Total Protein, Sodium, Potassium, CO2 (carbon dioxide, bicarbonate), Chloride, BUN (blood urea nitrogen), Creatinine, ALP (alkaline phosphatase), ALT (alanine amino transferase), AST (aspartate amino transferase), Bilirubin d Serum Protein Electrophoresis

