7.1 Sample Size Determination

When the sample size is 10, as planned in this pilot study, a single-group repeated measures analysis of variance with a 0.05 significant level will have 80% power to detect a difference in means across the 4 levels by an effect size of 0.32. Assuming a standard deviation at each level to be 2.2 and a between level correlation to be 0.6, the average difference will be detected in this scenario is 0.78.

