7.2 Statistical Methods

Descriptive Statistics

Primary Hypothesis: There is no difference in the number of clinically significant MM lesions detected by FDG PET/MRI, C11 PET/CT, C11 PET/MRI compared to the standard technique FDG PET/CT.

The patients will go through all of the 4 techniques and the number of clinically significant MM lesions detected by each technique will be collected. Our primary outcome is the number of MM lesions detected by each technique, which can vary from 0 to 13 with 5 or 6 lesions as an average for the MM patients. It is a repeated measures ANOVA design and our primary interest if to see if there is a within subject effect – if the number of MM lesions detected by each technique differ.

If the overall test is significant, post-hoc comparisons between the scores of the three new techniques (FDG PET/MRI, C11 PET/CT, C11 PET/MRI) and the standard technique (FDG PET/CT) will be carried out with Bonferroni correction for multiple comparison.

Secondary Hypothesis 1: There is no difference in the clarity scoring of the MM lesions among the 4 techniques.

The primary interest of Objective 2 is to compare the clarity of the detected MM lesions across the 4 techniques. A score demonstrating clarity of the lesion will be assigned to each detected lesion with higher score means clearer of the lesion image. One way repeated measure analysis of variance will be employed to detect if there is any difference among the average scores of detected MM lesion in each technique. If the overall test is significant, post-hoc comparisons between the scores of the three new techniques (FDG PET/MRI, C11 PET/CT, C11 PET/MRI) and the standard technique (FDG PET/CT) will be carried out with Bonferroni correction for multiple comparison.

Explore Objectives:

Explore which are the risk factors for having more MM lesions: CMP (Comprehensive Metabolic Panel) Glucose, Calcium, Proteins, Albumin, Total Protein, Sodium, Potassium, CO2 (carbon dioxide, bicarbonate), Chloride, BUN (blood urea nitrogen), Creatinine, ALP (alkaline phosphatase), ALT (alanine amino transferase), AST (aspartate amino transferase), Bilirubin;

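### The primary lesion count is not limited to the region that all four scans image, and neither scanner's range is stated

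*Combined protocol and SAP*

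**What the plan says.** Imaging Techniques, placed after 6.4 Day 3, sets out two acquisition protocols. The first is "PET/CT: Standard clinical Mayo Clinic whole-body PET/CT acquisition protocol". The second is "PET/MR: PET/MRI myeloma acquisition study protocol", followed by a task list with four stations and seven PET beds. That list is also labelled whole body. Neither entry gives an upper or lower anatomical limit.

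For the primary outcome, 7.2 says that "the number of clinically significant MM lesions detected by each technique will be collected", and describes this as a number "which can vary from 0 to 13 with 5 or 6 lesions as an average for the MM patients". The four counts per patient go into a one-way repeated measures ANOVA. If the overall test is significant, each of the three new techniques is compared with FDG PET/CT under a Bonferroni correction.

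No section limits the count to a region that all four scans cover, says how to treat a lesion that only some scans image, or asks for the range of each scan to be recorded.

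**The concern.** A raw count per technique depends on two things: how well the technique detects lesions, and how much of the body it images. Within one scanner protocol the second is roughly constant. Across two protocols it need not be. A lesion imaged by PET/CT but outside the PET/MRI range can add one to the PET/CT counts and can add nothing to the PET/MRI counts, and the reverse holds if PET/MRI reaches further.

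Two of the three planned comparisons cross scanners: FDG PET/MRI and C-11 acetate PET/MRI, each against FDG PET/CT. A consistent range difference would push both in the same direction and would not average out over patients. It would also enter the overall F-test that opens the way to the comparisons. Section 3.1 says the pilot is to guide a larger study, so a coverage effect read as a detection effect could carry forward into that design.

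**Working it through.** **Inputs from the plan.** Section 7.1: n = 10, k = 4 techniques, alpha 0.05, effect size 0.32, stated power 80%, SD 2.2, correlation 0.6, and an average difference of 0.78. Section 7.2: a mean of 5 or 6 lesions; 5.5 is used below, with 5 and 6 as the range.

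**Step 1: reproduce the plan's figure.** Section 7.1 claims "80% power to detect a difference in means across the 4 levels by an effect size of 0.32". Take the effect size as V / [SD² × (1 − correlation)], where V is the variance of the four means with divisor 4. The noncentrality is n × k × effect size = 10 × 4 × 0.32 = 12.8. A noncentral F with 3 and 27 degrees of freedom then gives power 80.6%, so the stated 80% is reproduced. Treating 0.32 as Cohen's f gives 70.4% (with the correlation adjustment) or 32.1% (without it), so the first form is the one in use.

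**Step 2: identify the 0.78.** SD² × (1 − 0.6) = 4.84 × 0.4 = 1.936. The standard deviation of the four means is √(0.32 × 1.936) = 0.787. Using 0.78 itself gives power 79.9%. So 0.78 matches the standard deviation of the four means, not a difference between two techniques.

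**Step 3: effect of a range difference.** This step rests on an assumption that is not in the documents: all four techniques detect equally well, but a share q of lesions lies outside both PET/MRI scans. Two techniques then average d = 5.5 × q fewer lesions than the other two. The variance of the four means is (d/2)², and the noncentrality is 40 × (d/2)² / 1.936.

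| Share q | d (mean 5.5) | Noncentrality | False-positive rate, mean 5.5 | Means 5 to 6 |
|---|---|---|---|---|
| 5% | 0.275 | 0.39 | 7.1% | 6.7–7.5% |
| 10% | 0.55 | 1.56 | 14.2% | 12.5–16.2% |
| 15% | 0.825 | 3.52 | 27.9% | 23.5–32.7% |
| 20% | 1.10 | 6.25 | 47.3% | 39.8–55.0% |
| 25% | 1.375 | 9.77 | 68.1% | 58.9–76.3% |

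The nominal rate is 5%. Only d² enters, so a PET/CT range that is shorter by the same d gives the same rates.

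**Step 4: share that equals the design effect.** Setting d/2 = 0.787 gives d = 1.574. Then 1.574 / 5.5 = 29% (26% for a mean of 6, 31% for a mean of 5).

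**Step 5: does a shared region remove the effect?** In a count simulation (20,000 runs, each technique detecting an imaged lesion with probability 0.8), raw counts gave false-positive rates of 8.7%, 20.9% and 63.6% at shares of 5%, 10% and 20%. These exceed the values in step 3 because the simulated correlation between techniques was about 0.74 with no lesions out of range, not 0.6. Counting only in the shared region kept the rate between 4.7% and 5.1% at every share from 0 to 30%.

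**The case against.** The strongest reply is that nothing shows a range difference. Both protocols carry the whole-body label, which suggests that equivalent coverage was intended. That stands: the effect is conditional, and its sign and size are unknown. The label does not settle the matter, because neither protocol states limits.

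A reader might infer from the seven-bed list that PET/MRI covers the same fixed length in every patient, whatever their height, and so falls short of PET/CT. The documents do not support this. They do not say that the number of beds is fixed, they give no bed length or overlap, and they give no PET/CT range to compare with. A reader might also infer that an out-of-range lesion is scored as missed. No such rule is written; a lower count is only what an unrestricted count would produce.

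It can also be said that scan limits are visible on stored images. Section 9.2 counts magnetic media and instrument data as source documents, and 9.4 requires retention, so a later restriction to a shared region is probably feasible. That stands too. But a counting region chosen once the counts are known is a post-hoc choice, which a rule set in advance avoids.

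Finally, coverage could be seen as part of a technique's yield. This carries less weight. Range is a scan setting, and the gain that 1.4 expects from PET/MRI is better detection of diffuse marrow infiltration, not a longer scan.

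**Conclusion.** The gap is real but conditional. The plan states neither scan range and does not confine the primary count to a region that all four scans image. If the ranges differ, the overall test and the two PET/MRI comparisons with FDG PET/CT cannot separate coverage from detection. The comparison of C-11 acetate PET/CT with FDG PET/CT uses one named PET/CT protocol and is largely unaffected.

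The size rests on assumed shares, equal true detection, and the plan's own mean, SD and correlation. A 5% share does little (about 7% against 5%). A 10% share nearly triples the false-positive rate (about 14%), and 20% brings it to about 47%.

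A reader might divide 0.78 by 5.5 and conclude that a 14% share already matches the difference the study is designed to detect. It does not: 0.78 corresponds to the standard deviation of the four means, and about 29% of lesions would have to be out of range to equal the full design effect. The power statement in 7.1 reproduces and is not in question here.

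**What to change.** Add a sentence to 7.2 stating that the primary count uses only lesions inside the anatomical region imaged by all four scans of that patient. Record the upper and lower limit of each scan with the read, and list lesions outside the shared region separately by technique. The rule is needed for the primary count only; the clarity score averages over detected lesions, so an out-of-range lesion does not enter it as a zero.

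The cost is one sentence and two entries per scan (2 × 4 scans × 10 patients = 80 entries), with no extra imaging. The small downside is that lesions outside the shared region leave the primary count, though they are still reported. If the ranges already match, the counts do not change and the record shows it.

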7.1 Sample Size Determination

When the sample size is 10, as planned in this pilot study, a single-group repeated measures analysis of variance with a 0.05 significant level will have 80% power to detect a difference in means across the 4 levels by an effect size of 0.32. Assuming a standard deviation at each level to be 2.2 and a between level correlation to be 0.6, the average difference will be detected in this scenario is 0.78.

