Number of Subjects	10				
Diagnosis and Main Inclusion Criteria	Clinically diagnosed multiple myeloma spectrum disease. Adult patients who are able to provide informed consent.				
Study Product, Dose, Route, Regimen	C-11 acetate, 10 mCi, intravenous injections				
Duration of Administration	Bolus injection				
Reference therapy	F-18 FDG				
Statistical Methodology	Objective 1. Repeated measures ANOVA. Univariate one-way repeated measures ANOVA F-test is used to calculate the sample size. Objective 2. One way repeated measure analysis of variance will be employed to detect if there is any difference among the average scores of detected MM lesion in each technique. When the sample size is 10, a single-group repeated measures analysis of variance with a 0.05 significant level will have 80% power to detect a difference in means across the 4 levels by an effect size of 0.32.				

1 Introduction

This document is a protocol for a human research study. This study will be carried out in accordance with the applicable United States government regulations and Mayo Clinic research policies and procedures.

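### The 0.78 that section 7.1 calls an average detectable difference is the standard deviation of the four technique means; the matching highest-to-lowest gap is about 1.6 to 2.2 lesions

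*Combined protocol and SAP*

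**What the plan says.** Section 7.1 fixes the sample at 10 and states that the repeated measures ANOVA, at the 0.05 level, "will have 80% power to detect a difference in means across the 4 levels by an effect size of 0.32". The Study Summary (Statistical Methodology) repeats that statement and names the univariate one-way repeated measures F-test as the basis of the calculation. Neither place defines the effect size.

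Section 7.1 then converts it to the lesion scale, using a common SD of 2.2 for every technique and a correlation of 0.6 between techniques. The result of that conversion is reported in these words: "the average difference will be detected in this scenario is 0.78". No pattern of means is given, and the term used for the 0.78 is not explained.

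Section 7.2 describes the outcome as a lesion count, "which can vary from 0 to 13 with 5 or 6 lesions as an average for the MM patients". It sets the follow-up comparisons as each of the three new techniques against FDG PET/CT, with Bonferroni correction.

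**The concern.** The 0.78 is the only figure in the plan that tells a reader, in lesions, what 10 patients can detect. Because the stated interest is in each new technique against FDG PET/CT, it will naturally be read as a gap in lesion count between techniques. On that reading the study is sensitive to about 14% of the average count (0.78/5.5, taking 5.5 as the midpoint of the plan's 5 or 6).

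An omnibus F-test, however, is powered on the spread of all four means, and a measure of spread is not a gap between two of them. If 0.78 is the spread, the detectable gap is larger than stated. A non-significant overall test could then be taken to exclude gaps that the study had little power to see. The figure could also be carried into the larger study that section 3.1 says this pilot is meant to guide.

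**Working it through.** **Inputs.** From section 7.1: n = 10, M = 4 techniques, alpha 0.05, power 80%, effect size 0.32, SD 2.2, correlation 0.6. From the Study Summary: univariate repeated measures F-test. Equal variances, equal correlations and approximate normality are assumed, consistent with the plan's single SD and single correlation.

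**Set-up.** Let V = Σ(μᵢ − μ̄)²/4 be the variance of the four technique means. The within-subject error variance is SD²(1 − ρ) = 4.84 × 0.4 = 1.936. The test has 3 and 27 df, critical value 2.960, and noncentrality λ = n × M × V/1.936 = 40V/1.936.

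**Which definition of 0.32 gives 80% power?**

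| Reading of 0.32 | λ | Power |
|---|---|---|
| V/[SD²(1 − ρ)] | 40 × 0.32 = 12.8 | 80.6% |
| Same, but V computed with divisor 3 | 30 × 0.32 = 9.6 | 67.2% |
| Cohen's f on SD 2.2: V = (0.32 × 2.2)² = 0.496 | 10.24 | 70.4% |
| √(V/1.936) | 40 × 0.1024 = 4.10 | 32.1% |

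Only the first reproduces the plan.

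**Where 0.78 comes from.** Exactly 80% power needs λ = 12.61, so the ratio is 12.61/40 = 0.315, which prints as 0.32. Then V = 0.3153 × 1.936 = 0.610 and √V = 0.781. That is the plan's 0.78. (Starting from the rounded 0.32, √V = 0.787.) The figure is therefore the standard deviation of the four means.

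**What that means as a gap.** At √V = 0.781:

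| Pattern of the four means | Largest gap / √V | Largest gap | Mean of six pairwise gaps |
|---|---|---|---|
| Two against two | 2 | 1.56 | 1.04 |
| One differs from three | 4/√3 = 2.309 | 1.80 | 0.90 |
| Evenly spaced | 6/√5 = 2.683 | 2.10 | 1.16 |
| Two extremes, two midway | √8 = 2.828 | 2.21 | 1.10 |

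For any four means the largest gap lies between 2√V and √8·√V, so 1.56 to 2.21 covers every pattern. Relative to 5.5 lesions this is 28% to 40%. The mean of the six gaps cannot fall below (2/√3)√V = 0.90.

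**If 0.78 really were a gap between techniques.** Taking it as the largest gap, in the same pattern order:

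| | V | λ | Power at n = 10 | n for 80% |
|---|---|---|---|---|
| Two against two | 0.152 | 3.14 | 25% | 37 |
| One differs | 0.114 | 2.36 | 20% | 48 |
| Evenly spaced | 0.085 | 1.75 | 15% | 64 |
| Two extremes | 0.076 | 1.57 | 14% | 71 |

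Simulation with 100,000 runs per pattern gives the same powers at 0.78, and 79.7% to 80.1% at the four 80%-power gaps. Taking 0.78 as the mean of all six gaps, power is 43% to 66%.

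For a single paired t-test, the SD of a difference is 2.2 × √(2 × 0.4) = 1.968. A true gap of 0.78 then has about 20% power at 0.05 and about 9% at 0.05/3.

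**The case against.** The best defence is that the plan says average, not largest, and that the average most relevant to its own comparisons is over the three gaps from FDG PET/CT, not all six. At V = 0.610 that average runs from 0.60 (one new technique differs) to 1.80 (FDG PET/CT alone differs). It is 0.74 when FDG PET/CT is one of the two midway means in the extremes pattern. So 0.78 lies inside the range, and if it were that average, power would run from 20% to 96%. This part stands as a caution: the wording could be true for some arrangement. It does not rescue the figure, because the plan states no arrangement, and 0.78 matches √V at exactly 80% power without needing one.

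Three further points have some weight:

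- The definition of the effect size is inferred, not printed, so the sponsor should confirm it against the original software output.
- In the two-against-two pattern 0.78 is each mean's distance from the grand mean, so the phrase may be loose wording for an average deviation. Even there the techniques differ by 1.56.
- The 14% to 25% powers and the 37 to 71 patients apply only if 0.78 is read as the largest gap. They show the cost of a misreading, not a shortfall in the planned study.

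It is also true that 0.78 drives no decision rule and did not set the sample size.

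**Conclusion.** The point holds. Sample size, power, effect size, SD and correlation agree with one another, but 0.78 is mislabelled: it is the standard deviation of the four technique means. At 80% power for the overall test, the highest-to-lowest gap is 1.56 to 2.21 lesions (1.80 if one technique differs), 2.0 to 2.8 times the printed figure. This rests on the plan's SD of 2.2, its correlation of 0.6 taken as equal for all pairs, and the only definition tried that returns the stated 80%. A range is the right answer because the plan gives no pattern of means. This should be fixed because it is the plan's sole lesion-scale statement of sensitivity, but it does not undermine the design.

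**What to change.** Once the definition has been confirmed against the original calculation, replace the last sentence of section 7.1 with wording such as:

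> Effect size 0.32 is V/[SD²(1 − ρ)], where V is the variance of the four technique means. With SD 2.2 and correlation 0.6 this is a standard deviation of about 0.78 among the four means, that is, a difference between the highest and lowest technique of about 1.6 to 2.2 lesions depending on the pattern (about 1.8 if one technique differs). The 80% power applies to the overall F-test.

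Define the effect size in the Study Summary too. Read there as Cohen's f, the same inputs give 70% power, not 80%.

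Optionally, add a detectable difference for the comparisons with FDG PET/CT. For 80% power at 0.05/3 it is about 2.1 lesions with the pooled ANOVA error (27 df) or 2.4 with separate paired t-tests (9 df). Name the test assumed, since section 7.2 specifies only Bonferroni-corrected post-hoc comparisons.

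The cost is wording in two places and a less favourable stated sensitivity. No more patients are needed, and neither the design nor the analysis changes.

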7.2 Statistical Methods

Descriptive Statistics

Primary Hypothesis: There is no difference in the number of clinically significant MM lesions detected by FDG PET/MRI, C11 PET/CT, C11 PET/MRI compared to the standard technique FDG PET/CT.

The patients will go through all of the 4 techniques and the number of clinically significant MM lesions detected by each technique will be collected. Our primary outcome is the number of MM lesions detected by each technique, which can vary from 0 to 13 with 5 or 6 lesions as an average for the MM patients. It is a repeated measures ANOVA design and our primary interest if to see if there is a within subject effect – if the number of MM lesions detected by each technique differ.

If the overall test is significant, post-hoc comparisons between the scores of the three new techniques (FDG PET/MRI, C11 PET/CT, C11 PET/MRI) and the standard technique (FDG PET/CT) will be carried out with Bonferroni correction for multiple comparison.

Secondary Hypothesis 1: There is no difference in the clarity scoring of the MM lesions among the 4 techniques.

The primary interest of Objective 2 is to compare the clarity of the detected MM lesions across the 4 techniques. A score demonstrating clarity of the lesion will be assigned to each detected lesion with higher score means clearer of the lesion image. One way repeated measure analysis of variance will be employed to detect if there is any difference among the average scores of detected MM lesion in each technique. If the overall test is significant, post-hoc comparisons between the scores of the three new techniques (FDG PET/MRI, C11 PET/CT, C11 PET/MRI) and the standard technique (FDG PET/CT) will be carried out with Bonferroni correction for multiple comparison.

Explore Objectives:

Explore which are the risk factors for having more MM lesions: CMP (Comprehensive Metabolic Panel) Glucose, Calcium, Proteins, Albumin, Total Protein, Sodium, Potassium, CO2 (carbon dioxide, bicarbonate), Chloride, BUN (blood urea nitrogen), Creatinine, ALP (alkaline phosphatase), ALT (alanine amino transferase), AST (aspartate amino transferase), Bilirubin;

SPEP (Serum Protein Electrophoresis). Immunoglobulins, Serum Free light chains; Bone marrow biopsy % and beta-2-microglobulin level (if obtained). Linear regression model with correlated data (the MM lesions detected by each technique) will be utilized to investigate the association between the potential risk factors and the number of MM lesions detected for each patient.

Handling of Missing Data

Since our sample size is 10, and they will get their imaging done in two days, we don't anticipate any missing data.

Multiplicity

We only have one primary outcome for our primary research interest. There will be no concern of multiple testing for the overall group testing. But if we see an overall effect and we will do post-hoc comparisons of the numbers of detected MM lesions between the three new techniques (FDG PET/MRI, C11 PET/CT, C11 PET/MRI) and the standard technique (FDG PET/CT). Bonferroni correction for multiple comparison will be used to address multiplicity issue.

Interim Analysis

There will not be interim analysis for our study.

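### The lesion-count plan states no sphericity correction and no error term for the comparisons with FDG PET/CT; with paired standard errors the F-test gate is unnecessary

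*Combined protocol and SAP*

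**What the plan says.** The primary hypothesis in section 7.2 is that lesion counts do not differ for FDG PET/MRI, C-11 PET/CT and "C11 PET/MRI compared to the standard technique FDG PET/CT". The outcome is a count "which can vary from 0 to 13 with 5 or 6 lesions as an average for the MM patients". The test is introduced with "It is a repeated measures ANOVA design and our primary interest if to see if there is a within subject effect".

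The comparisons with FDG PET/CT are conditional: "If the overall test is significant, post-hoc comparisons between the scores of the three new techniques" and the standard are made, Bonferroni-corrected. The Multiplicity paragraph repeats this order ("if we see an overall effect and we will do post-hoc comparisons of the numbers of detected MM lesions") and adds: "Bonferroni correction for multiple comparison will be used to address multiplicity issue".

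Section 7.1 sizes the overall test at 80% power with n=10 and effect size 0.32: "Assuming a standard deviation at each level to be 2.2 and a between level correlation to be 0.6". The Study Summary calls the F-test univariate, but only in describing the sample-size calculation. No section mentions sphericity, an epsilon correction, or the error term for the follow-up comparisons.

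**The concern.** One common correlation is a strong assumption for these four scans. Under section 6.2 both FDG scans come from a single injection, back to back. Under section 6.3 the two acetate scans share a tracer and normally a day. The section 6.5 footnotes allow that day to fall up to 14 days after Day 1. Scans may therefore correlate more within a tracer than across tracers, or may cluster by scanner.

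Two things then depend on details that the plan leaves open. An uncorrected F-test rejects too often when correlations are unequal. The Bonferroni comparisons control family-wise error if each uses its own paired standard error, but may not if they use the pooled ANOVA error. With paired errors the comparisons need no protection from the F-test, so the gate can only block an answer to the stated objective: which technique finds more lesions than FDG PET/CT.

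**Working it through.** **Inputs from the documents.** n=10, four techniques, alpha 0.05, effect size 0.32, SD 2.2, correlation 0.6, average difference 0.78 (section 7.1). Assumptions: two-sided tests, and every correlation other than 0.6, written same-tracer/cross-tracer.

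**1. The plan's own figure.** Read the effect size as (variance of the four means)/(SD² × (1−ρ)). Then λ = 10 × 4 × 0.32 = 12.8, and the noncentral F with 3 and 27 df gives 80.6% power. Starting from 0.78 instead: 0.78²/(2.2² × 0.4) = 0.608/1.936 = 0.314, power 79.9%. The 80% reproduces. If one technique alone differs by d, the variance of the means is 3d²/16; setting this to 0.32 × 1.936 = 0.620 gives d = 1.82 lesions.

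**2. What unequal correlation does.** Let w be the same-tracer and c the cross-tracer correlation. The within-subject contrasts have variances proportional to 1−w, 1−w and 1+w−2c, and ε = (sum)²/(3 × sum of squares). At 0.8/0.5: 1.2²/(3 × 0.72) = 0.67. At 0.9/0.45: 1.2²/(3 × 1.02) = 0.47. The SD of a paired difference is 2.2 × √(2(1−ρ)). The mean correlation is 0.6 in all three rows, so the pooled error always implies 2.2 × √0.8 = 1.97.

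| Correlation | ε | SD, FDG PET/MRI minus FDG PET/CT | SD, either C-11 scan minus FDG PET/CT | SD implied by pooled error |
|---|---|---|---|---|
| 0.6 throughout | 1.00 | 1.97 | 1.97 | 1.97 |
| 0.8/0.5 | 0.67 | 1.39 | 2.20 | 1.97 |
| 0.9/0.45 | 0.47 | 0.98 | 2.31 | 1.97 |

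Under clustering the pooled error is too small for the acetate comparisons and too large for FDG PET/MRI.

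**3. Error rates under the global null.** Simulation: multivariate normal, 100,000 data sets per setting, comparisons at 0.05/3, per cent.

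| Correlation | F uncorrected | F Greenhouse-Geisser | Paired, no gate | Paired, gate | Pooled, no gate | Pooled, gate |
|---|---|---|---|---|---|---|
| 0.6 | 5.0 | 3.4 | 4.7 | 2.3 | 4.4 | 3.0 |
| 0.8/0.5 | 7.2 | 4.6 | 4.4 | 2.6 | 5.5 | 4.6 |
| 0.9/0.45 | 9.4 | 5.1 | 4.0 | 2.6 | 6.5 | 6.1 |

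Milder clustering (0.7/0.55 or 0.8/0.7) gives an F-test size of about 5.6%. Holm has the same global-null error as Bonferroni because its first step is the same.

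**4. Power for FDG PET/MRI against FDG PET/CT.** Paired Bonferroni, without vs with the gate, 60,000 data sets per setting, per cent.

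| True pattern (lesions) | 0.6 | 0.8/0.5 | 0.9/0.45 |
|---|---|---|---|
| FDG PET/MRI alone +1.82 | 53 vs 51 | 86 vs 73 | 99 vs 80 |
| FDG PET/MRI alone +1 | 15 vs 12 | 32 vs 16 | 62 vs 22 |
| Acetate +1.82 and MRI +1, additive | 15 vs 15 | 32 vs 31 | 62 vs 57 |
| Acetate +1 and MRI +1, additive | 15 vs 15 | 32 vs 26 | 62 vs 44 |

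If scans cluster by scanner instead (same scanner 0.8, otherwise 0.5), the loss moves: C-11 PET/CT alone +1 falls from 32 to 16%, while FDG PET/MRI alone +1 goes from 11.8 to 11.2%. If both acetate scans gain 1.82 and FDG PET/MRI is unchanged, the gate costs each acetate comparison 0.6 points or less at 0.6, 0.8/0.5 and 0.9/0.45.

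**5. Holm.** At 0.6, with acetate +1.82 and MRI +1, ungated Holm against the plan's gated Bonferroni gives 27 vs 15% (FDG PET/MRI), 62 vs 52% (C-11 PET/CT) and 93 vs 91% (C-11 PET/MRI). Most of this gain comes from Holm, not from dropping the gate.

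**6. Count data.** With values around 5.5 rounded and limited to 0-13, the F-test size is 5.0, 7.1 and 9.2% in the three settings. At 0.8/0.5, FDG PET/MRI alone has 82 vs 70% (+1.82) and 29 vs 15% (+1).

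**The case against.** The plan can be defended on several grounds, and much of the defence stands.

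- A reader might infer that the F-test addresses the wrong hypothesis. It does not. No difference of three techniques from FDG PET/CT is the same null as equality of all four means. An overall test followed by Bonferroni is coherent and, with paired errors, conservative. What the F-test cannot say is which technique differs, and that is what the objective in section 2 asks.
- A reader might infer that the plan commits to an uncorrected univariate F-test. The documents do not support this: that word describes only the sample-size calculation. The supportable statement is that the correction and the error term are unspecified.
- A reader might infer that type I error is inflated, or that the gate is costly, as planned. The only documented correlation is 0.6, and there neither holds. The schedule makes clustering plausible but does not give its size, or say whether it follows tracer or scanner.
- The large power losses need an isolated gain. Section 1.4 cites a comparison in which acetate PET had 84.6% sensitivity against 57.7% for FDG, so an acetate gain is the expected pattern, and under it the gate costs little at 0.8/0.5.
- Making the comparisons primary replaces a test with 80% power by comparisons with less. That is true and has to be stated in section 7.1.
- This is a ten-patient pilot. That limits the consequences, but the plan chose formal tests, a power claim and a multiplicity rule, so those should be fully specified.

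**Conclusion.** The concern holds in limited form. The missing sphericity correction and error term are real gaps: under assumed but plausible clustering they decide whether the overall test runs at 5% or at 7 to 9%, and whether family-wise error stays below 5% or reaches about 6.5%. With pooled errors and strong clustering, the gate does not repair this (about 6.1%).

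With paired errors the gate adds no needed protection, because Bonferroni and Holm hold under any correlation. Its cost is small in most patterns: about 1 to 3 points at 0.6 for a single differing technique. With acetate +1.82 and MRI +1, it costs FDG PET/MRI about 1 point at 0.8/0.5 and 5 points at 0.9/0.45. It is large only if scans cluster and a technique in the FDG PET/CT cluster gains alone. Since the correlations are unknown before the data, the decision rule should not depend on them.

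Every figure away from 0.6 rests on assumed correlations and an SD of 2.2, and nothing was computed for the clarity score. This should be changed before analysis; it does not invalidate the design.

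**What to change.** **Section 7.2, the Multiplicity paragraph and the Study Summary.** For lesion count, test the three comparisons with FDG PET/CT by paired t-tests, each with its own paired standard error, using Holm at an overall 0.05 and no gate. Report the within-subject F-test with Greenhouse-Geisser correction as supportive.

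**If the sponsor keeps the overall test as primary,** still specify Greenhouse-Geisser, paired standard errors and Holm. At 0.6 this keeps most of the gain. A corrected gate blocks more, though: for FDG PET/MRI alone +1 at 0.8/0.5, Bonferroni power falls from 16 to 11%.

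**Section 7.1.** State that 80% applies only to the uncorrected overall test under equal correlation. With one technique differing by 1.82 lesions, the Greenhouse-Geisser test has about 75% at 0.6, 68% at 0.8/0.5 and 60% at 0.9/0.45. Add the power of the comparisons at 0.6. One Bonferroni paired comparison at 1.82 lesions has a difference SD of 1.97, noncentrality 1.82 × √10/1.97 = 2.92 on 9 df, and about 53% power. If both acetate scans gain 1.82, at least one success has about 71%, against 91% for the overall test.

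**Clarity score.** Its hypothesis is "There is no difference in the clarity scoring of the MM lesions among the 4 techniques", so keep the overall test, with Greenhouse-Geisser and paired standard errors for the follow-up comparisons. This is advice for consistency only.

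**Cost.** Wording only; no extra patients or scans. Dropping the gate does not cure the low power of single comparisons, which comes from n=10.
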